8 ACUTE HIV-1 INFECTION (AHI) TESTING

This section has been defined in a separate statistical analysis plan (A5354_AHIDdiag_Statistical_Analysis_Plan_v1.0_6MAR2020, dated Mar. 6, 2020).

9 STUDY STATUS AND LOSS TO FOLLOW-UP

CONSORT-style diagrams will be developed for the primary analysis summarizing key components of the study follow-up of the study population.

9.1 Study Status and Completeness of Follow-up of Participants

Table: Number (%) for the following categories:

- i. 'Completed Step 1 as defined by the protocol' or 'On study' (for interim analyses).
- ii. "Off study" due to death.
- iii. "Off study" prior to end of Step 1 follow-up (or, at interim analyses, prior to data retrieval date) for reasons other than death (with subcategories showing reason and whether or not prior to week 48 on Step 1).

Listing: Showing all premature discontinuations with centralized Fiebig Stage result, site, timing and reason of premature discontinuation, week of last clinic visit, ARV regimen taken, and whether a sample was collected at the week 48/49 visit.

9.2 Duration of Follow-up Achieved

Table: Time (weeks) from study entry to last visit reported: median, 25th and 75th percentiles, minimum, and maximum.

NOTE: At the primary analysis, all analyses from here onwards will be undertaken after any exclusions from analyses. Participants who are determined to be Fiebig Stage VI by centralized testing will be followed and presented until they are taken off study at week 24.

10 PREGNANCY OUTCOMES

Listing: Site, study week of pregnancy outcome, pregnancy outcome, estimated week of conception, gestational age at pregnancy outcome, ART taken from study entry/pregnancy onset to time of pregnancy outcome (showing also week of changes in ART, if any).

Listing (if available): Other pregnancy outcome information collected.

11 ANTIRETROVIRAL THERAPY STATUS

Table: summarizing the ART regimen initiated at entry: number (%) [may be included in baseline table]

Table: summarizing number (%) of participants who have stopped ART treatment (No holds ≥ 7 days; Hold ≥ 7 consecutive days), reason(s) for stopping, and whether the participant permanently discontinued or temporarily interrupted ART prior to, at, or after week 48.

Table: summarizing the reasons (if any) for participants that modified their ARV regimen, along with the timing and reason for the change.

NOTE: Participants who interrupt ART for ≥ 7 consecutive days will be considered for withdrawal from the study. If the ART interruption occurs prior to study week 24 on Step 1 and the participant has not previously demonstrated an HIV-1 RNA < 50 copies/mL (prior to the hold lasting ≥ 7 consecutive days), then the participant will be withdrawn from the study and undergo the premature study discontinuation evaluation.

12 ADVERSE EVENTS

The protocol requires grading of events according to The Division of AIDS Table for Grading the Severity of Adult and Pediatric Adverse Events (DAIDS AE Grading Table), corrected Version 2.1, July 2017, which can be found on the DAIDS RSC website at <http://rsc.tech-res.com/clinical-research-sites/safety-reporting/daids-grading-tables>.

The protocol makes the following reporting requirements for signs and symptoms:

“At Step 1 entry, signs and symptoms of all grades that occurred within 30 days prior to entry must be recorded as medical history. Post-entry Grade ≥ 3 signs and symptoms and all signs and symptoms that led to a change in ART, regardless of grade”

The protocol makes the following reporting requirements for laboratory test abnormalities:

“At Step 1 entry, record all protocol-required laboratory values (performed by local laboratories) with exception of the urinalysis, regardless of grade. For post-entry assessments, record all laboratory values for creatinine, CrCl, AST (SGOT), and ALT (SGPT) regardless of grade. Post-entry Grade ≥ 2 laboratory findings and all laboratory findings that led to a change in ART, regardless of grade”

NOTE: Creatinine clearance should be graded using the categorical mL/min values from the DAIDS 2.1 toxicity grading tables, which begins with values below 90 mL/min. The percent change criteria will not apply to A5354. In Step 2, only creatinine clearance greater than Grade 2 should be reported.

The protocol makes the following reporting requirements for diagnoses:

“At Step 1 entry, all diagnoses that are described in protocol section 6.3.4 (Acute HIV-1, bone fractures, coronary heart disease, cancer, diabetes, tuberculosis, chronic hepatitis B or C, renal disease) must be recorded as medical history. Post-entry, record all targeted diagnoses (see list on the A5354 PSWP) and diagnoses that led to a change in ART.

NOTE: Uterine pregnancy does not require reporting as an AE (unless other SAE criteria are met) but must still be recorded in the eCRFs.”

Additionally, all AEs meeting the SAE definition or EAE reporting requirements, or led to a change in study treatment, must be reported.

For the purpose of ongoing safety monitoring occurring within A5354, the following data summaries will be provided at each interim analysis, separately for Step 1 and Step 2:

Table: summarizing number (%) of participants and the adverse events reported in the database, by MedDRA SOC, PT, grade and study group.

Table: summarizing number (%) of participants and the serious adverse events reported in the database, by MedDRA SOC, PT, grade and study group.

Note: For participants enrolled to Step 2, AEs on Step 1 will be summarized up to last study visit on Step 1 in the primary analysis report of Step 1. Any AEs reported after the last visit on Step 1 prior to entry to Step 2 will be summarized in the analysis for Step 2 long-term follow-up.

13 CD4/CD8 CELL COUNTS

Summaries at each measurement week:

Table: CD4+, CD8+ cell count (cells/mm³): N, mean, standard deviation, median and 25th and 75th percentiles, min, max;

Table: Change from baseline (calculated as FU-BL) in CD4+, CD8+ cell count (cells/mm³): N, mean, standard deviation, median and 25th and 75th percentiles, min, max

Table: CD4/CD8 ratio: N, mean, standard deviation, median and 25th and 75th percentiles, min, max.

Table: Fold change from baseline (calculated as FU/BL) in CD4/CD8 ratio: N, mean, standard deviation, median and 25th and 75th percentiles, min, max

14 STANDARD HIV-1 RNA AND VIROLOGIC FAILURE

Summaries of HIV-1 RNA at each measurement week:

Table: HIV-1 RNA viral load (log₁₀ copies/mL): N, mean, standard deviation, median and 25th and 75th percentiles, min, max; number (%) by category (<50, ≥50; and separately for <200 copies/mL and ≥200 copies/mL)

Table: 95% confidence interval based on exact binomial distribution on proportion of HIV-1 RNA < 50 or 200 copies/mL at each study week.

Plot: Proportion of participants with HIV-1 RNA <50 or 200 copies/mL by study week, overall and by Fiebig group

Summaries/Listing of confirmed virologic failure:

Table: Number of participants with confirmed virologic failure (defined as two consecutive HIV-1 RNA >200 copies/mL at Step 1 week 24 or later or at any time after achieving HIV-1 RNA <50 copies/mL);

Listing: (For participants with confirmed virologic failure) Initial failure week and HIV-1 RNA copies/mL, confirmed failure week and HIV-1 RNA copies/mL, ART regimen at the time of initial/confirmed failure, duration of ART regimen at the time of failure, Fiebig stage/study group

15 PROCEDURE SUMMARY (INTERIM)

Table summarizing:

- a. Number (%) of participants who consented and successfully completed each optional procedure
- b. Number (%) of participants consenting to and receiving multiple procedures
- c. Summary of week the procedure(s) was consented to and week the procedure was performed: N, median, 25th and 75th percentiles, min, max

16 DATA COMPLETENESS SUMMARY (INTERIM)

To be generated and provided by Frontier Sciences, the Data Management Center.

Will contain summaries of completeness of collection for following study data:

- a. Serum creatinine, creatinine clearance
- b. AST, ALT
- c. CD4+/CD8+
- d. Plasma HIV-1 RNA

Specimens for:

- e. Fiebig Staging
- f. HIV-1 Genotype
- g. Total HIV-1 DNA by qPCR
- h. PBMC and Plasma Storage [only if large volume blood draw or leukapheresis are not done]
- i. Large Volume Blood Collection [as an alternative to leukapheresis]
- j. Leukapheresis [optional procedure]
- k. Gut biopsy [optional procedure]
- l. Lumbar Puncture [optional procedure]

NOTE: Routine PBMC and plasma storage will be obtained from the large volume blood collection (or optional leukapheresis) at entry. Stored PBMC and plasma will be obtained at weeks 60 and 72, only if optional leukapheresis or large volume blood collection is not performed at those visits.

17 PRIMARY OUTCOME MEASURE

The primary outcome measure defined in the protocol, section 10.2.1:

Cell-associated HIV-1 DNA (CAHD) in 5 million blood-derived CD4+ T-cells (assayed by quantitative PCR [qPCR]) at week 48 on Step 1

Note: Derivation of the primary outcome measures and any contributing datasets will be double-coded in accordance with the CBAR SOP, PROG.10083.

For interim analyses, a summary of the availability of CA-DNA results will be generated.

Table: Number (%) of participants with a week 48 visit on Step 1; Number (%) of participants with available CAHD results at week 48 on Step 1; Number (%) of participants not reaching week 48 on Step 1

17.1 Primary Efficacy Analyses

Note: Programs related to the analysis of the primary outcome measures listed in this section will require validation in accordance with the CBAR SOP, PROG.10083, including independent verification of results

A table summarizing completeness of the primary outcome measure, and reasons for missing data (if any) will be provided, overall and by study group.

Analysis of the primary outcome measure will be restricted to participants who maintain HIV-1 RNA <50 copies/mL at week 48 with no ART interruption of ≥ 7 consecutive days and have available CAHD results from week 48 or week 49. Specifically, plasma HIV-1 RNA by commercial assay must be <50 copies/mL at week 48 with no prior virologic failure (defined as having two consecutive HIV-1 RNA >200 copies/mL at week 24 or later or at any time after achieving HIV-1 RNA <50 copies/mL). This study is designed to evaluate the effect of suppressive ART initiated in different stages of AHI on the establishment and persistence of HIV-1 reservoirs; this is the rationale for analyzing HIV-1 DNA only among virally suppressed participants and not in those with incompletely suppressed viremia (≥ 50 copies/ml).

Participants who are excluded from the primary analysis will be presented in a listing, which displays the criteria by which they were excluded.

The primary outcome measure will be summarized as a binary outcome, [0 copies] versus [>0 copies] of CAHD per 5 million CD4+ T-cells, assessed separately and jointly by gag- and integrase-assays. In order for a participant to be considered as having 0 copies of CAHD, the participant must be found to have an undetectable CAHD result from both assays. The proportion of participants with '0 copies of CAHD' will be compared pairwise between groups using Fisher's exact test. A 95% confidence interval for the proportion estimated will be calculated using the exact binomial distribution. The analysis groups will be the study groups: Group 1 (Fiebig I/II), Group 2 (Fiebig III/IV), and Group 3 (Fiebig V), as defined by the results of the centralized testing from samples at study entry.

CAHD per million CD4+ T-cells will also be summarized as a continuous variable, separately for gag- and integrase-assays, presenting N, median, Q1 and Q3 for the raw CAHD values (by study group and separately by Fiebig Stage). CAHD per 5 million CD4+ T-cells will be divided

by 5 in order to evaluate CAHD per million CD4+ T-cells. Undetectable CAHD results will be imputed as 0.01 copies. Additionally, summaries will be provided for log₁₀-transformed CAHD per million CD4+ T-cells for gag- and integrase-assays, which will present N, mean, standard deviation, median, Q1, Q3 and min/max. Plots showing median, Q1 and Q3 values over time will also be presented, overall and by study group. In addition, scatter plots of gag- vs. integrase-assays will be presented with study groups marked with separate symbols.

A supplemental analysis will use Wilcoxon rank sum test to compare the primary outcome measure on the continuous scale, separately for gag- and integrase-assays, between pairwise study groups (and between select Fiebig stages). An additional supplemental analysis will use the Jonckheere–Terpstra test to assess potential trends across the study groups (and between Fiebig stages). We will also examine the primary outcome measure that includes participants with extended periods of ART interruption (≥ 7 consecutive days) who maintained HIV-1 RNA < 50 copies/mL at week 48. For clades with sufficient data, supplemental sensitivity analyses will compare Fiebig stages stratified by HIV subtype.

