For the purpose of this study, a S/CO ratio ≥ 10 is considered “positive” in the ARCHITECT assay. However, a S/CO of between 0.5 and 10 that corresponds to HIV-1 p24 antigen positive AHI represents between 4-5.5 \log_{10} HIV-1 RNA copies/mL [30]. Therefore, HIV-1 p24 antigen detection at a S/CO of 0.5 may correspond to approximately 6,000 HIV-1 RNA copies/mL (Figure 2.1-4 below), which is well above the lower limit of assay detection for commercial assays. Participants with a previous ARCHITECT S/CO ratio of < 0.5 who now have a value ≥ 1.0 are eligible to enroll in the study pending the HIV-1 RNA determination. Potential participants with S/CO > 0.5 but < 10 will require a positive HIV-1 RNA results prior to enrollment (this criterion will decrease the incidence of false-positive HIV-1 infection).

[figure not shown]

Figure 2.1-4. The log₁₀ linear relationship between the HIV-1 RNA copies/mL of plasma (abscissa) and the ARCHITECT assay S/CO values (ordinate)

Challenges

The majority (19/23, 83%) of the ACTG international laboratories have an Abbott m2000 system available, 10/23 (43%) also have the Roche COBAS TM, and most of the laboratories conduct HIV-1 RNA testing on-site. However, the turn-around-times (TAT) for results is highly variable from <24 hours up to 14 days even for on-site testing. The average TAT is 4.6 days and the median is 3 days. These times are independent of instrument; i.e., if it takes 2 days for results at one laboratory on the Roche COBAS TM, it also takes 2 days for results at the same laboratory using the Abbott m2000 system. Inclusion criteria for this study are designed to identify individuals during AHI while accommodating differences in testing at various study sites. Fiebig staging will be performed using standardized processes at reference laboratories on samples collected on the day of study entry.

PCR Assay for Detection of CAHD and Cell-associated RNA in CD4+ T-cells

A qPCR assay with single-copy sensitivity targeting a highly conserved region of integrase in the HIV-1 *pol* gene [33] will be used to detect HIV-1 DNA or RNA in 5 million total CD4+ T-cells.

Antiretroviral Regimen

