NOTE: If an HIV-1 resistance genotype is performed as part of clinical care during screening or any time on the study ([section 6.3.2](#)), the site investigator may use this information to guide a change in ART, if clinically indicated, including a change from the study-provided ARV regimen to a non-study-provided ARV regimen or a change from a non-study-provided ARV regimen to the study-provided ARV regimen.

Total HIV-1 DNA

CAHD will be assayed by qPCR in 2 million CD4+T-cells from the **Step 1** entry time point **in participants who have undetectable CAHD at week 48** to ensure that each participant's viral DNA can be amplified by the qPCR assay. This will exclude false negative results for HIV-1 DNA detection at the primary endpoint (week 48) resulting from PCR primer mismatch or other inhibitors of PCR in the participant's sample.

Total HIV-1 DNA will be obtained either from the stored PBMC and plasma or large volume blood collection (or optional leukapheresis).

Primary Endpoint Determination

Please refer to the A5354 LPC for instructions related to the collection, processing, and shipping of these samples.

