4.3 Analysis Populations

All participants enrolled to the study will be included in accrual and centralized Fiebig result summaries.

Participants found to be HIV negative after enrollment will not be included in any summaries except those stated above. Participants found to be in Fiebig Stage VI will have baseline and select follow-up data summarized from the period of time prior to going off study (Week 24).

Analysis of the primary outcome measure will be restricted to study groups 1-3 (as determined by centralized testing), and only for participants who maintain HIV-1 RNA <50 copies/mL at week 48 with no ART interruption of ≥ 7 consecutive days and have available CAHD results from week 48 or week 49. Sensitivity analyses will include participants with extended periods of ART interruption (≥ 7 consecutive days) that maintained HIV-1 RNA <50 copies/mL at week 48.

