18.2 Cell-associated HIV-1 DNA in participants prior to ART initiation

Pre-ART cell-associated HIV-1 DNA will be summarized using the same approach as week 48 CAHD.

Fold-changes (absolute change in the log₁₀-transformed measurements) from pre-ART measurement in CAHD will be summarized using a similar approach.

Correlations between selected immunology responses (IFNg+ and total response) and week 48 CAHD will be examined using Spearman correlation coefficient (primary analysis population) with and without controlling for the study group.

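### The protocol says an entry-sample qPCR check will exclude false-negative week-48 zeros, but no analysis rule in protocol 10.6 or SAP 4.3/17.1 uses the result

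*SAP*

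**What the plan says.** Protocol 6.4.9 (Total HIV-1 DNA) describes a qPCR check on 2 million CD4+ cells drawn at Step 1 entry. The check is run only "in participants who have undetectable CAHD at week 48". The section gives the aim plainly: "This will exclude false negative results for HIV-1 DNA detection at the primary endpoint (week 48) resulting from PCR primer mismatch". It names PCR inhibitors as a second cause.

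The analysis text is silent on it:

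- **0-copies rule (SAP 17.1, same rule in protocol 10.6).** "the participant must be found to have an undetectable CAHD result from both assays". No entry-sample condition is attached.
- **Analysis population (SAP 4.3, repeated in 17.1).** Besides viral suppression and uninterrupted ART, participants must "have available CAHD results from week 48 or week 49".
- **Supplemental and sensitivity analyses (SAP 17.1).** These are Wilcoxon and Jonckheere-Terpstra tests, a run that adds participants with long ART interruptions, and a subtype run: "For clades with sufficient data, supplemental sensitivity analyses will compare Fiebig stages stratified by HIV subtype". None uses the entry result.
- **Secondary outcome (SAP 18.2).** "Pre-ART cell-associated HIV-1 DNA will be summarized using the same approach as week 48 CAHD", with fold-changes from entry. This is a summary and does not validate a week-48 zero.

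**The concern.** A zero is the favourable outcome in the primary comparison. The protocol recognises that a zero can be an assay failure and says it has a safeguard. The statistical sections then define the endpoint without the safeguard.

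SAP 4.5 and 17 require the primary derivation to be programmed twice, independently. Take a participant who is undetectable on both assays at week 48 and also undetectable at entry. A programmer who follows SAP 17.1 literally codes 0 copies. One who follows the aim of 6.4.9, or who takes an available result to mean a laboratory-valid one, drops the participant. If the choice is left until such cases appear, it will be made with the data in view.

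It is also unclear which assays the entry check covers. Protocol 2.1 describes "A qPCR assay with single-copy sensitivity targeting a highly conserved region of integrase in the HIV-1" *pol* gene, and 6.4.9 speaks of a single qPCR assay, while the endpoint uses gag and integrase.

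**Working it through.** **1. What the two-assay rule already covers.** A mismatch that defeats only one target does not create a joint zero, because the other assay should still detect DNA. A joint false zero needs both assays to fail. For the entry check to reveal it, the failure must also be present in the entry sample. The separate gag and integrase summaries lack this protection: one failed target gives an undetectable value, imputed as 0.01 copies in SAP 17.1.

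**2. Baseline.** Inputs from protocol 10.4: 42 per group; zero rates 75% (I/II), 25% (III/IV) and 3.5% (V); Fisher's exact test at 0.05 per pair, taken here as two-sided. Full enumeration gives 76.3% power for 65% v 35% (stated 76%) and 99.7% for 75% v 25% (stated >95%). For 25% v 3.5% it gives 77.9% against a stated 80%; an uncorrected normal approximation gives 81.7%. The baseline used below is 77.9%.

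**3. Effect of an assumed failure rate.** Let f be the chance that a participant who has DNA reads zero on both assays, equal across groups. The documents give no value, so f is an assumption.

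Apparent zero rate = p + f(1 − p). Chance of at least one false zero among 42 in Fiebig V = 1 − (1 − 0.965f)^42.

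| f | III/IV v V power | I/II v III/IV power | Expected false zeros in V | Chance of ≥1 in V |
|---|---|---|---|---|
| 0 | 77.9% | 99.7% | 0 | 0 |
| 0.25% | 77.0% | 99.7% | 0.10 | 10% |
| 1% | 74.4% | 99.7% | 0.41 | 33% |
| 2% | 71.0% | 99.6% | 0.81 | 56% |
| 5% | 61.4% | 99.4% | 2.03 | 87% |

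I/II v V stays above 99.9% throughout. The 0.25% row corresponds to two independent 5% failures (0.05 × 0.05). The larger rows need failure shared by the two assays.

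**4. One participant in III/IV v V.** Expected zeros are 42 × 0.25 = 10.5 and 42 × 0.035 = 1.47. Two-sided Fisher p-values near those counts:

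- 10/42 v 2/42: p = 0.026.
- One false zero added in V, 10/42 v 3/42: p = 0.067.
- That participant excluded, 10/42 v 2/41: p = 0.026.
- One false zero in each group, 11/42 v 3/42: p = 0.038, so no reversal.

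**5. What exclusion could cost in Group 1.** Suppose a share g of true Group 1 zeros is also undetectable in 2 million entry cells, and none in III/IV. An assumed mean of 2 copies per 2 million cells gives g = exp(−2) = 13.5%; 20% is a second assumed value.

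- Excluded: rate = 0.75(1 − g)/(1 − 0.75g) = 72.2% or 70.6%; I/II v III/IV power about 99% or 98%.
- Counted as >0: rate = 0.75(1 − g) = 64.9% or 60.0%; power 95.6% or 88.9%.

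**The case against.** The strongest reply is that the check is a laboratory procedure. A laboratory that withholds a failed result makes it unavailable, so the population rule would remove it, and SAP 17.1 already plans a table of reasons for missing data and a listing of exclusions. The laboratory processing chart cited in 6.4.9 is not among the documents, so this cannot be ruled out. A reader might infer that the safeguard affects no planned analysis; the documents do not support going that far. SAP 18.2 also pairs each participant's entry and week-48 values through fold-changes. Still, where this SAP wants an assay-control exclusion it writes one: the notes to 18.1 discard T-cell results when the active control falls below background. The primary outcome has no such rule.

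Second, the 0-copies sentence can be read as a necessary condition, leaving room for others. That is fair, but no other condition is stated.

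Third, the two-assay rule removes most primer mismatch from the joint endpoint, and an entry check cannot see inhibition confined to the week-48 sample. Both points stand, and they narrow the exposure.

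Fourth, SAP 18.2 gives entry CAHD the week-48 approach, which implies both assays. This weakens the doubt about gag but does not settle what 6.4.9 requires. It also exposes a mismatch: 6.4.9 tests entry samples only for week-48 zeros, while SAP 2.7.2, Table 1 and 18.2 place no such limit on entry CAHD.

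**Conclusion.** The concern holds in a limited form. The protocol states a safeguard for the primary endpoint that its own analysis section and the SAP do not carry through, and the coding of an unverified zero is left open. This should be settled before the primary analysis.

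The size cannot be determined from the documents. A reader might infer from the power table that the trial is materially underpowered because of false zeros. That is not supported: every f is assumed, and the independent-failure case costs 0.9 points in one of three contrasts. The I/II contrasts, which carry the main hypothesis, are essentially unaffected. The practical exposure is III/IV v V, where so few zeros are expected in V that one participant's coding can move p across 0.05. The fix would not recover power; it would show whether a result rests on unverified zeros.

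**What to change.** 1. Reconcile protocol 6.4.9 with protocol 10.6 and SAP 17.1. Either amend 6.4.9 to say the check flags unverified zeros and does not exclude them, keeping the dual-undetectable rule for the primary analysis, or carry the exclusion into the 0-copies rule. Changing 10.6 alone would leave the protocol contradicting itself.
2. State that the entry check is run on both gag and integrase, and reconcile its restriction to week-48 zeros in 6.4.9 with SAP 2.7.2, Table 1 and 18.2.
3. List week-48 zeros by study group and HIV subtype, showing undetectable and missing entry results separately.
4. Add one sensitivity analysis that repeats the pairwise Fisher tests and exact confidence intervals under the alternative handling (flagged zeros excluded, if the primary analysis keeps them), for the joint endpoint and for each assay.

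The cost is wording in two documents, one listing and one extra run. The entry testing is largely planned already; any part of it not yet planned on both assays would be added laboratory work. The downside is interpretive. An undetectable result in 2 million entry cells does not prove assay failure, least of all in very early infection. Exclusion can only lower a group's zero rate and may drop true Group 1 zeros (step 5 of the working). If flagged zeros are also counted as >0 copies, label that run a worst-case bound only.

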10.4 Sample Size and Accrual

The primary study objective is to compare the primary outcome measure at week 48 **on Step 1** after ART dichotomized as: 0 versus >0 copies of CAHD in 5 million blood-derived CD4+ T-cells. The groups are expected to differ in likelihood that a participant has no detectable total HIV-1 DNA, with percentages estimated to be:

Fiebig I/II: 75%
Fiebig III/IV: 25%
Fiebig V: <5%

Forty-two (42) virologically suppressed participants at week 48 **on Step 1** per group will provide high power to detect differences between all three groups based on this primary endpoint: >95% power for Fiebig I/II versus III/IV, >95% power Fiebig I/II versus V and 80% power for Fiebig III/IV versus V (assuming 3.5% for Fiebig V participants), based on Fisher's exact test with type I error rate of 0.05 for each pairwise comparison. Table **10.4-1** below shows power for the comparison between Fiebig I/II versus III/IV with different underlying probability of undetectable cell-associated HIV-1 DNA at week 48 with 42 participants per group. The study will have moderate power (76%) to detect a difference between the two groups even with higher estimated probability in Fiebig III/IV group (35%) and lower estimated probability in Fiebig I/II group (65%).

Table **10.4-1**: Power Comparisons

Fiebig I/II	Fiebig III/IV		
	25%	30%	35%
75%	>95%	>95%	95%
70%	>95%	95%	88%
65%	95%	88%	76%

It is further assumed that 90% of participants who initiate study treatment will remain HIV-1 RNA <50 copies at week 48 for primary endpoint evaluation. Taking into account a

15% lost to follow-up rate and insufficient samples at primary outcome week, the total sample size is **196 (a target enrollment of 50 per group)**.

NOTE: Groups 2 and 3 closed to enrollment under protocol Version 1.0.

The sample size increase to 196 participants is intended to aid in meeting the accrual target for Group 1 and increase the number of early-treated participants engaged in the cohort that are potentially eligible for future studies. This is an estimation of the additional number of participants that will need to be enrolled in order to fully accrue Group 1 (since group assignment is unknown at the time of enrollment), based on the current rate of participants who were estimated to be in Group 1, and determined to be in Group 1 at study entry after centralized testing.

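### Fisher's exact test is valid but conservative for the primary pairwise comparisons; Boschloo's test recovers some power within the same 5%, and no interval is planned for any between-group difference

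*SAP*

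**What the plan says.** SAP 17.1 reduces the primary outcome to 0 versus more than 0 copies of CAHD. The proportion with 0 copies "will be compared pairwise between groups using" Fisher's exact test. Protocol 10.6 names the same test. SAP 18 carries the approach over to binary secondary outcomes.

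Protocol 10.4 bases power on Fisher's test with "type I error rate of 0.05 for each pairwise comparison". It does not say whether the test is two-sided. It states "80% power for Fiebig III/IV versus V", "assuming 3.5% for Fiebig V participants" and 25% for III/IV, with 42 evaluable participants per group.

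The only interval planned for the binary outcome is for each group's own proportion: a 95% "confidence interval for the proportion estimated will be calculated using the exact binomial distribution". Neither document plans an estimate or interval for a difference between groups, and neither mentions an unconditional exact test.

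**The concern.** Fisher's test conditions on the total number of participants with 0 copies. With about 40 per group and one rate near zero, the conditional p-value takes few values, so the true error rate falls below the nominal one. Power is lost on III/IV versus V, the comparison for which the plan claims the least power. Boschloo's test takes the Fisher p-value as its statistic and calibrates it over all possible common rates. It therefore keeps the 5% guarantee and gives back part of the loss.

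The missing interval is a separate gap. The primary objective is to compare groups, yet the primary binary analysis yields three p-values and three single-group intervals. A non-significant III/IV versus V result would not show what difference had been excluded.

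**Working it through.** **Inputs.** Protocol 10.4: 42 evaluable per group; rates of 0 copies of 75% (I/II), 25% (III/IV) and 3.5% (V); 0.05 per pair; target 50 per group; 90% suppressed; 15% lost or with insufficient sample; 63 enrolled in Group 2 and 54 in Group 3. Assumption: two-sided tests, because sidedness is not stated.

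**Formulas.**
- Power = Σx Σy Bin(x; n₁, p₁) · Bin(y; n₂, p₂) · 1[reject at (x, y)], summed over every outcome pair.
- Size at a common rate π is the same sum with p₁ = p₂ = π. Maximum size is taken over a grid of 1,999 values of π.
- Two-sided Fisher p = sum of the conditional probabilities no larger than the observed one.
- Boschloo: reject when Fisher p ≤ c, where c is the largest cut-off with maximum size ≤ 0.05. At 42 v 42, c = 0.0732. Because c exceeds 0.05, the rejection region contains Fisher's.

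**The plan's own figures.** All nine cells of Table 10.4-1 reproduce with Fisher's test (65% v 35%: 76.3%, stated 76%). The III/IV versus V figure does not: Fisher gives 77.9% at 42 per group and first shows 80.1% at 44. A pooled normal approximation gives 81.7%, but that is not the named test.

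**Evaluable numbers.** 50 × 0.85 = 42.5, so 42 allows for the 15% loss only. 50 × 0.85 × 0.90 = 38.25, or 38. Reported enrolment gives 63 × 0.765 = 48 and 54 × 0.765 = 41.

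**III/IV versus V, 25% v 3.5%.**

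| Evaluable | Fisher | Boschloo | Boschloo maximum size |
|---|---|---|---|
| 38 v 38 | 71.2% | 77.3% | 4.4% |
| 40 v 40 | 74.7% | 80.1% | 4.8% |
| 42 v 42 | 77.9% | 82.6% | 4.8% |
| 48 v 41 | 83.3% | 83.8% | 4.7% |

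At 48 v 41, Fisher with doubled smaller tails gives 78.4%, so the gain is 0.5 or 5.4 points depending on a convention that neither document states. With equal groups the two definitions give the same power.

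In counts at 42 per group: if Group 3 has no one at 0 copies, Fisher needs 6 in Group 2 and Boschloo 5. If Group 3 has one, they need 8 and 7.

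**I/II versus III/IV.** At 75% v 25% and 42 per group, both tests give 99.7%. At 65% v 35%: 76.3% to 76.7% at 42 v 42, 68.0% to 73.0% at 38 v 38, and 74.0% to 79.3% at 38 v 48.

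**True size at 42 v 42.**

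| Common rate | Fisher | Boschloo |
|---|---|---|
| 3.5% | 0.15% | 0.72% |
| 14.25% (mean of 25% and 3.5%) | 2.60% | 3.73% |
| 25% | 3.00% | 4.38% |
| Maximum | 3.75% | 4.82% |

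**Family-wise error.** With all three groups at a common rate and 42 each, the chance of at least one rejection is 1 − Σ bᵢbⱼbₖ over the outcomes in which no pair rejects (b = binomial probability). At 25% it is 7.6% with Fisher and 10.8% with Boschloo. The maxima on a grid of rates are 9.4% and 11.9%.

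**The case against.** The strongest reply is that nothing in the plan is wrong. Fisher's test is valid and is named consistently for power and for analysis, and the whole of Table 10.4-1 reproduces with it. Preferring another exact test is a choice about efficiency. That stands.

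Three further points also stand.
- Groups 2 and 3 enrolled more than 50. At 48 v 41, Fisher already has 83.3% under the summed-probability definition, so little remains to be gained there.
- The three comparisons are unadjusted. Fisher's conservatism is the only slack in that family, and Boschloo's test uses part of it.
- The missing interval does not depend on the choice of test.

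A reader might infer that Fisher's test wastes most of its 5%. The planning figures do not support that: at the mean III/IV–V rate it spends 2.6%, so just under half goes unused. It spends less than half of the 5% only at common rates below about 13% (or above about 87%), and Boschloo's test also spends little at the low planning rate of 3.5%. A reader might also infer that Boschloo's test restores the planned 80% in general. It does at 40 and 42 per group, does not at 38 (77.3%), and is barely needed at 48 v 41 unless Fisher's tails are doubled.

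The reply does not remove three things: the stated 80% is about two points above what the named test gives at the stated size; the two-sided definition is open; and no between-group difference is estimated.

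**Conclusion.** The point holds as an efficiency and reporting improvement. It does not challenge validity. For III/IV versus V, Boschloo's test adds 4.7 points at the planned 42 per group, 6.1 at 38, and 0.5 or 5.4 at 48 v 41 depending on the Fisher definition, with error at or below 5% per comparison throughout. For I/II versus III/IV the gain is negligible at the planning rates. At 65% v 35% it is under half a point at 42 v 42 and about 5 points at 38 v 38 or 38 v 48.

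These figures assume two-sided tests and the protocol's rates, and they are sensitive to those rates: at 20% v 3.5% and 42 per group, Fisher gives 55.7% and Boschloo 63.6%. The 38, 48 and 41 assume that the 15% and 90% allowances both apply and are the same in every group.

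**What to change.** Make these changes before CAHD is tabulated by group.

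1. In Protocol 10.6 and SAP 17.1, add the three pairwise differences in proportion with exact unconditional 95% confidence intervals, and name the method. This is worth doing whichever test is used.
2. Amend Protocol 10.6 and SAP 17.1 together to name Boschloo's exact test at two-sided 0.05 per comparison, and state how the two-sided p-value is formed. SAP 18 follows for binary secondary outcomes. Keep the Fisher p-value as a footnote. Changing the SAP alone would leave the two documents in conflict on the primary test.
3. If Fisher's test is kept, state its sidedness and two-sided definition, and restate the III/IV versus V power in Protocol 10.4 as 78% at 42 per group.

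The cost is wording and a standard software call, with no added participants. There are two downsides. The test is less familiar to readers. Using more of each 5% also raises the unadjusted family-wise error (7.6% to 10.8% at a common rate of 25%), so the text should say that error is controlled per comparison only.
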